#### **10.6.12 Exposure to Investigational Product**

Descriptive statistics will be produced to describe the exposure of SC and oral investigational product by randomized treatment group for subjects exposed to investigational product for the double-blind period and open-label period, respectively. The total ALN exposure for the subject randomized to ALN arm will also be provided.

#### **10.6.13 Exposure to Concomitant Medication**

Types of concomitant medications will not be summarized.

### **10.7 Endpoints From Sub-study**

#### **10.7.1 Bone Turnover Marker and Biomarker**

The subset described in [Section 7.8.2](#) and [7.8.3](#) will be used for the analyses of percent change in bone turnover markers and biomarkers. These include values, changes from baseline, and percent changes from baseline at month 1, 3, 6, ,9, 12, 15, 18, 24, and 36 in P1NP, sCTX, BSAP, OC and sclerostin. The Wilcoxon rank-sum test as described in [Section 10.5.1.7](#) will be used for treatment comparisons for percent change in bone turnover markers or biomarkers. In addition, percent changes from baseline at post-baseline visits in iPTH and serum sclerostin level will be provided.

#### **10.7.2 BMD by DXA**

The subset described in [Section 7.8.1](#) will be used for the analyses of percent changes in lumbar spine, total hip and femoral neck BMD by DXA. Percent changes from baseline at months 6, 12, 18, and 24 in DXA BMD will be compared between treatment groups using a repeated measures model as described in [Section 10.5.1.2](#) and an ANCOVA model described in [Section 10.5.1.5](#) with treatment group, baseline BMD, machine type and interaction of baseline BMD and machine type as independent variables. Any missing value during the 12-month double-blind ALN-controlled study period will be imputed by carrying forward the last non-missing post-baseline value prior to the missing value. Descriptive summary of observed DXA values at Month 36 will be provided.

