**10.1.6.6 Analysis Set for Imaging and PK/BTM/Biomarker Sub-study**

The analysis set for BTM/Biomarker includes all randomized subjects who undergo BTM/biomarker sampling during the study. Subjects will be analyzed according to their randomized treatment assignments. The analysis set for imaging includes all randomized subjects who undergo additional imaging procedures during the study. Subjects will be analyzed according to their randomized treatment assignments. The PK analysis set includes all randomized subjects who undergo PK sampling during the study and who have received  $\geq 1$  dose of romosozumab.

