#### **Lumbar Spine BMD by DXA and BMD and estimated bone strength by QCT in the Sub-study**

**Lumbar spine BMD and estimated bone strength measured in the sub-study will be summarized by visit using the same approach as described for the main study.**

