## **7.8 Analysis Subsets for Imaging and Pharmacokinetics (PK) / Bone Turnover Marker (BTM) / Biomarker Sub-study**

### **7.8.1 Sub-study Imaging Efficacy Analysis Set**

The respective subset includes all randomized subjects who enrolled in the sub-study and have a baseline and  $\geq 1$  post-baseline evaluation at or before the time point under consideration and will be used to evaluate vBMD, bone strength measure by FEA and DXA BMD. Subjects will be analyzed according to their randomized treatment assignment.

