## 10.5 Efficacy Analyses

The age stratification factor will be included in the statistical models when analyzing data from the entire study but will not be included in analyses of sub-study.

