#### **10.5.1.2 Standard Analyses for Ordinal Endpoints**

All ordinal endpoints will be summarized using the number and percent of subjects in each category by treatment group. Unless otherwise specified, the percentages will be based on the subjects with non-missing observations. Treatment comparisons on ordinal endpoints will be done using a repeated measures proportional odds model adjusting for age strata and presence or absence of severe vertebral fracture at baseline, visit and treatment by visit interaction. The odds ratios and their corresponding 95% 2-sided Wald confidence interval will be provided (SAS code in [Section 13.4.5](#)).

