### 10.7.3 vBMD by QCT and Lumbar Spine Strength by FEA

The primary efficacy subset described in [Section 7.8.1](#) will be used for the analyses of percent changes from baseline in for integral (total) and trabecular volumetric BMD by QCT and lumbar spine strength by FEA. Percent changes from baseline at months 6, 12, and 24 in QCT vBMD and lumbar spine strength will be compared between treatment groups using a repeated measures model as described in [Section 10.5.1.2](#) and an ANCOVA model described in [Section 10.5.1.5](#) with treatment group and baseline vBMD as independent variables. Any missing value during the 12-month double-blind ALN-controlled study period will be imputed by carrying forward the last non-missing post-baseline value prior to the missing value.

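### The sub-study imaging section of the SAP cites an ordinal model for continuous BMD changes, lets blood-only women into the DXA comparison at Months 12 and 24 only, and omits main-study covariates without declaring it

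*SAP*

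**What the plan says.** **Model.** SAP 10.7.2 covers four visits (Months 6, 12, 18 and 24). It states that percent changes "in DXA BMD will be compared between treatment groups using a repeated measures model as described in"; the section it then names is 10.5.1.2. It also specifies the ANCOVA of 10.5.1.5. SAP 10.7.3 states that percent changes "in QCT vBMD and lumbar spine strength will be compared between treatment groups using a repeated measures model as described in"; it names the same section, again with the ANCOVA. Section 10.5.1.2 reads: "Treatment comparisons on ordinal endpoints will be done using a repeated measures proportional odds model". Its output is an odds ratio.

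**Analysis set.** The SAP 7.8.1 imaging set "includes all randomized subjects who enrolled in the sub-study and have a baseline and" at least one later evaluation, and it serves vBMD, FEA and DXA BMD alike. SAP 6.2 defines sub-study enrolment by signature of the sub-study consent. Protocol 10.1.6.6 is narrower: "The analysis set for imaging includes all randomized subjects who undergo additional imaging procedures during the study".

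**Covariates.** SAP 10.5 puts the age stratum in main-study models "but will not be included in analyses of sub-study". Sections 10.5.1.5 and 10.5.1.6 repeat that exclusion but keep severe vertebral fracture at baseline. The ANCOVA covariates listed in 10.7.2 and 10.7.3 include neither. For lumbar spine BMD and bone strength, Protocol 10.5.2.1 says that what is "measured in the sub-study will be summarized by visit using the same approach as described for the main study". The main-study BMD model in that section includes both the age stratum and severe vertebral fracture.

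**Declared changes.** SAP Section 11 lists one change from the protocol: fracture type instead of fracture location in the pain analysis.

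**The concern.** A percent change in BMD is continuous. A programmer who follows the cross-reference reaches the ordinal model and its code, which cannot estimate a difference in mean percent change. The reference also conflicts with the SAP's own rule, because the 10.5.1.2 model adjusts for age strata and 10.5 removes age from sub-study analyses.

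The purpose of the imaging component is the course of response over 24 months. If the Month 12 and Month 24 comparisons draw on a larger and partly different group of women than Months 6 and 18, an apparent change between visits can partly reflect who was included. Precision would also appear to change for the same reason.

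Age is the only stratification factor at randomisation. In a subset of about 100 women not stratified in its own right, leaving it out gives up a cheap protection against chance imbalance.

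**Working it through.** The plan states no sample size or power for the sub-study, so there is no figure to reproduce. The check is mainly a comparison of sections.

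**1. Model reference.** The SAP draws the distinction correctly elsewhere. Main-study BMD (10.5.3.3) and the EQ-5D-5L VAS (10.5.4) cite 10.5.1.6; the ordinal EQ-5D-5L dimensions (10.5.4) cite 10.5.1.2. Section 10.5.1.6 includes DXA machine-type terms and its own sentence on the sub-study. The reference in 10.7.2 and 10.7.3 is therefore almost certainly a slip for 10.5.1.6.

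**2. Who has DXA, and when.**

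| Visit | Protocol section | Imaging women | Blood-only women |
|---|---|---|---|
| Baseline | 7.2.1, 7.3.1 | yes | yes |
| Month 6 | 7.3.7 | yes | not scheduled |
| Month 12 | 7.3.13 | yes | yes |
| Month 18 | 7.3.15 | yes | not scheduled |
| Month 24 | 7.3.16 | yes | yes |

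Protocol 3.1 plans about 200 women in the sub-study and about 100 in imaging:

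- Blood-only: 200 − 100 = about 100.
- Possible blood-only share of the SAP 7.8.1 DXA set at Months 12 and 24: 100/200 = 50%.
- Standard error at Months 12 and 24 relative to an imaging-only set: √(50/100) = 0.71, assuming equal SD, 1:1 allocation and no missing data.

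For lumbar spine at Month 12, using the SDs in Protocol Tables 2 and 3, the pooled SD is √((6.0² + 3.5²)/2) = 4.91. The standard error of the treatment difference is 4.91 × √(2/50) = 0.98 points with 50 per arm and 4.91 × √(2/100) = 0.69 with 100 per arm. SAP 10.5.1.5 fits each time point separately, so this step would appear in the table between Months 6 and 12.

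Blood-only women have no scheduled QCT, so vBMD and FEA membership does not change.

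**3. Covariates.**

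| Source | Age stratum | Severe vertebral fracture |
|---|---|---|
| Protocol 10.5.2.1, main-study BMD | in | in |
| SAP 10.5.1.5 and 10.5.1.6, sub-study | out | in |
| SAP 10.7.2 and 10.7.3, ANCOVA lists | not listed | not listed |

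The documents do not give the share p of women aged 75 or older, so it is assumed. With 50 per arm, the SD of the between-arm difference in that share is √(2p(1 − p)/50):

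- p = 0.20: √(2 × 0.16/50) = 0.08.
- p = 0.50: √(2 × 0.25/50) = 0.10.

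A chance imbalance of about 8 to 10 percentage points is therefore one SD.

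**4. Cost of the two terms.** By a plain count with 100 women, the DXA ANCOVA as listed has 5 parameters (intercept, treatment, baseline, machine type, interaction), leaving 95 degrees of freedom. Adding two binary covariates leaves 93.

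**The case against.** The strongest reply is that this is a wrong section number and some loose wording in analyses that no confirmatory claim depends on. Much of that stands.

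- A reader might infer that the sub-study time course cannot be read, or that all its results are on the wrong scale. The documents do not support this. The ANCOVA in the same sentences gives a least-squares mean difference at each visit. Nor does the wrong reference contradict the protocol, which specifies no repeated measures model for sub-study imaging.
- A reader might infer that blood-only women contaminate the imaging analyses generally. They do not reach QCT or FEA and have no scheduled DXA at Months 6 and 18, the only DXA time points that SAP 4.5 lists as sub-study endpoints. SAP 2.5, 4.5, 13.1.1.3 and 13.1.1.4 all refer to the imaging component, so the intent is visible. But 7.8.1, the section that defines the set, does not say so.
- A reader might infer that omitting age flatly breaches the protocol. The SAP states the omission three times, so it is deliberate, and an unadjusted analysis remains valid. The protocol sentence speaks of summarising, covers lumbar spine BMD and bone strength, is silent on hip sites and names no covariates. The conflict is an inference. Severe fracture is an ambiguity within the SAP rather than a clear removal.
- The numerical effect of an age imbalance is probably small. If BMD response differed by 1 to 2 points between age strata (an assumption), a 10-point imbalance would shift the treatment difference by 0.1 to 0.2 points. The planned lumbar spine difference at Month 12 is 13.1 − 5.1 = 8.0.

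What remains is that the repeated measures model is wrong as written, the set is wider than the protocol's, and the covariate choices are inconsistent and undeclared.

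**Conclusion.** The point holds as a matter of specification. The repeated measures reference in 10.7.2 and 10.7.3 is wrong; the ANCOVA beside it is sound in scale. The 7.8.1 set departs from Protocol 10.1.6.6 and makes the DXA visits not like-for-like. The figures of up to about 200 women and a 50% blood-only share are upper bounds: they use the planned enrolment numbers, full attendance and the literal consent-based definition. The covariate part is the weakest: declaring and justifying the omission would be enough, though adjustment is the better choice at so low a cost.

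The effect is confined to sub-study endpoints. They are not in the testing sequence of SAP 10.1 and 13.5, and the Month 12 and 24 BMD endpoints in that sequence are analysed in the main study under 10.5.3.3. No primary or key secondary conclusion changes.

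**What to change.** 1. In SAP 10.7.2 and 10.7.3, cite 10.5.1.6 for the repeated measures model.
2. In SAP 7.8.1, require participation in the imaging component, in line with Protocol 10.1.6.6.
3. Include the age stratum and the severe-fracture term in the sub-study imaging ANCOVA and repeated measures models. This means amending 10.5, 10.5.1.5, 10.5.1.6, 10.7.2 and 10.7.3 together: changing only the last two would leave the other three still excluding age. Alternatively, keep the shorter models, make the severe-fracture wording consistent, and declare both omissions in Section 11 with a reason.

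The full set of edits touches six SAP sections and needs no new data. The costs are that blood-only women's DXA results appear only in the main-study analysis, and that each added covariate uses 1 degree of freedom.

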### 10.7.3 vBMD by QCT and Lumbar Spine Strength by FEA

The primary efficacy subset described in [Section 7.8.1](#) will be used for the analyses of percent changes from baseline in for integral (total) and trabecular volumetric BMD by QCT and lumbar spine strength by FEA. Percent changes from baseline at months 6, 12, and 24 in QCT vBMD and lumbar spine strength will be compared between treatment groups using a repeated measures model as described in [Section 10.5.1.2](#) and an ANCOVA model described in [Section 10.5.1.5](#) with treatment group and baseline vBMD as independent variables. Any missing value during the 12-month double-blind ALN-controlled study period will be imputed by carrying forward the last non-missing post-baseline value prior to the missing value.

### 10.7.4 PK

Serum concentration data described in [Section 7.8.4](#) will be provided to PKDM group for analyses. Details regarding objectives, data handling, and methodology of the analysis will be provided in a separate analysis plan.

## 11. Changes From Protocol-Specified Analyses

Protocol [Section 10.5.2.1](#) specified a logistic regression model adjusting for fracture location and potentially other factors impacting the pain score to analyze the incidence of subjects with a clinical meaningful improvement in worst pain. Fracture type is used as a covariate instead of the fracture location.

### 13. Appendices

#### 13.1 Technical Detail and Supplemental Information Regarding Statistical Procedures and Programs

##### 13.1.1 Visit Windows

Per protocol, all monthly study visits up to Month 13 have a  $\pm 7$ -day window. Following the 12-month double-blind ALN-controlled study period, study visits have a  $\pm 14$ -day window. To allow for variations in scheduling, the following sets of visit windows will be used to assign evaluations to a most appropriate nominal visit for analysis. Furthermore, there will be no gaps between visit windows in order to include as many data points as possible for summarization.

Regardless of the width of the visit window, if more than 1 visit falls within the defined window, the result from the visit closest to the target day will be used. If 2 evaluations are of the same distance from the target day, the result from the later visit will be used. If more than one evaluation on the same date and time, the average of the results will be used. Only laboratory results collected from the central laboratory will be averaged in the case of duplicate results. Results not included for analysis will be included in listings only.

For LOCF imputation, the last evaluation on or prior to the upper bound of the specified window (ie, no lower bound) would be used for each nominal visit.

The window for the monthly phone contact in between clinic visits throughout the study is  $\pm 7$  days. The window for the end of primary analysis period phone call is  $-14$  days to end of primary analysis. Unscheduled follow-up clinic visits after the monthly phone contact have a  $+ 21$ -day window. The window for the end of study phone contact is  $-14$  days to  $+ 7$  days.

##### 13.1.1.1 Spine X-ray

Nominal Visit	Target Day	Window Definition (Study Day)
Baseline a	1	Last evaluation prior to or on Study Day 1
Month 12	366	Study Day 2 to End of Double-blind Period Date
Month 24	731	End of Double-blind Period Date +1 to End of Open-label M24 Study Period Date
Month 36	1096	End of Open-label M24 Study Period Date +1 to Study Day 1278
Month 48	1461	Study Day 1279 to 1643
Month 60	1826	Study Day 1644 to 2008

a If results from baseline x-ray are not available, the results from scan taken on or before Study Day 14 will be considered baseline values.

Lateral spine X-rays are collected every 12 months after M36 until the end of the primary analysis period.

### 13.1.1.2 DXA (lumbar spine and proximal femur) for All Subjects

Nominal Visit	Target Day	Window Definition (Study Day)
Baseline a	1	Last evaluation prior to or on Study Day 1
Month 12	366	Study Day 2 to End of Double-blind Period Date + 30
Month 24	731	End of Double-blind Period Date + 31 to End of Open-label M24 Study Period Date + 30
Month 36	1096	End of Open-label M24 Study Period Date + 31 to Study Day 1278
Month 48	1461	Study Day 1279 to 1643
Month 60	1826	Study Day 1644 to 2008

a If results from baseline DXA are not available, the results from scan taken on or before Study Day 14 will be considered baseline values and not the Month 12 values.

DXA of lumbar spine and proximal femur are collected every 12 months after M36 until the end of the primary analysis period.

### 13.1.1.3 DXA (lumbar spine and proximal femur) for imaging component of Sub-study

Nominal Visit	Target Day	Window Definition (Study Day)
Baseline a	1	Last evaluation prior to or on Study Day 1
Month 6	183	Study Day 2 to 274
Month 12	366	Study Day 275 to End of Double-blind Period Date + 30
Month 18	548	End of Double-blind Period Date +31 to Study Day 639
Month 24	731	Study Day 640 to End of Open-label M24 Study Period Date +30
Month 36	1096	≥ Study Day End of Open-label M24 Study Period Date +31

a If results from baseline DXA are not available, the results from scan taken on or before Study Day 14 will be considered baseline values and not the Month 6 values.

### 13.1.1.4 QCT for imaging component of Sub-study

Nominal Visit	Target Day	Window Definition (Study Day)
Baseline a	1	Last evaluation prior to or on Study Day 1
Month 6	183	Study Day 2 to 274
Month 12	366	Study Day 275 to End of Double-blind Period Date + 30
Month 24	731	≥ End of Double-blind Period Date +31

a If results from baseline QCT is not available, the results from scan taken on or before Study Day 14 will be considered baseline values and not the Month 6 or Month 12 values.

**13.1.1.5 OC and BSAP for Sub-study**

Nominal Visit	Target Day	Window Definition (Study Day)
Baseline	1	Last evaluation prior to or on Study Day 1 before dosing
Month 1	31	Study Day 2 to 61
Month 3	92	Study Day 62 to 137
Month 6	183	Study Day 138 to 229
Month 9	275	Study Day 230 to 320
Month 12	366	Study Day 321 to End of Double-blind Period Date

**13.1.1.6 BTM (Excluding OC and BSAP) or Biomarker for Sub-study**

Nominal Visit	Target Day	Window Definition (Study Day)
Baseline	1	Last evaluation prior to or on Study Day 1 before dosing
Month 1	31	Study Day 2 to 61
Month 3	92	Study Day 62 to 137
Month 6	183	Study Day 138 to 229
Month 9	275	Study Day 230 to 320
Month 12	366	Study Day 321 to End of Double-blind Period Date
Month 18	548	End of Double-blind Period Date +1 to Study Day 639
Month 24	731	Study Day 640 to End of Open-label M24 Study Period Date
Month 36	1096	End of Open-label M24 Study Period Date+1 to Study Day 1278
Month 48	1461	Study Day 1279 to 1643
Month 60	1826	Study Day 1644 to 2008

Data are collected every 12 months after Month 36 until the end of the primary analysis period.

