#### **7.1.1 Study Visit Definitions**

The screening date is defined as the date the ICF is signed. The enrollment date is defined as the date of randomization. Randomization must be completed within 35 days of the screening date, or if the subject is rescreened per [Section 7.2.2](#) or [Section 7.2.3](#), within 35 days of the rescreening date.

Day 1 is defined as the day the first dose of romosozumab/placebo is administered. All on-study (post Day 1) visits are to be calculated from the Day 1 visit. If a subject's visit is delayed, their subsequent visit date is not to be shifted, and is always to be calculated from the Day 1 visit. Month is defined as a calendar month.

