### 7.3.14 Month 15 ( $\pm$ 14 Days) for Sub-study Subjects Only

#### For subjects participating in the Imaging and PK/BTM/Biomarker sub-study

- Nonvertebral and suspected clinical vertebral fracture reporting
- Adverse event and concomitant medications data collection
- Fasting blood sample for P1NP and sCTX
- Blood sample for sclerostin and iPTH
- Blood sample (serum and plasma) for novel biomarker development

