#### **4.5 Imaging and PK/BTM/Biomarker Sub-study Endpoints**

*During the 12-month double-blind ALN-controlled study period:*

- Romosozumab serum concentrations at Day 1, Months 1, 3, 6, 9, and 12
- Percent change from baseline in P1NP, BSAP, OC, and sCTX at Months 1, 3, 6, 9, and 12
- Percent change from baseline in iPTH and sclerostin at Months 1, 3, 6, 9, and 12
- For subjects participating in the imaging components:
  - Percent change from baseline in integral (total) and trabecular vBMD at the lumbar spine by QCT at Months 6, and 12
  - Percent change from baseline in lumbar spine strength as assessed by FEA at Months 6, and 12
  - Percent change from baseline in DXA BMD at the lumbar spine, total hip, and femoral neck at Month 6

*During the primary analysis period:*

- Percent change from baseline in P1NP and sCTX at Months 15, 18, 24, and 36
- Percent change from baseline in iPTH and sclerostin at Months 15, 18, 24, and 36
- For subjects participating in the imaging components:
  - Percent change from baseline in integral (total) and trabecular vBMD at the lumbar spine by QCT at Months 24

- Percent change from baseline in lumbar spine strength as assessed by FEA at Months 24
- Percent change from baseline in DXA BMD at the lumbar spine, total hip, and femoral neck at Month 18

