## Visit Windows

Based on protocol, all monthly study visits through Month 12, during the 12-month double-blind ALN-controlled study period, have a  $\pm 7$ -day window. The study visits during the open-label ALN study period, have a  $\pm 14$ -day window. Study procedures for a specific visit may be completed on multiple days as long as all the procedures are completed within the visit window. To allow for variations in scheduling, the analysis visit windows defined in [section 13.1.1](#) will be used to assign evaluations to a most appropriate nominal visit for analysis and summarization.

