#### **End of Double-blind Period Date**

End of the double-blind period date is defined as the following:

1. First open-label ALN dose date if this date is prior to or on Study Day 366 + 30 days
  2. Month 12 visit date if subject did not receive the open-label ALN prior to or on Study Day 396 and this date is prior to or on Study Day 396 days
  3. End of study day or Study Day 396, whichever occurs first, for subjects who did not complete the Month 12 visit prior to study day 396 days
- The Month 12 visit date is defined as the latest assessment collected at Month 12.

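### The SAP's visit-window table for bone turnover markers has no Month 15 row, so the stated Month 15 marker endpoints receive no result

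*SAP*

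**What the plan says.** **Endpoints.** SAP 4.5 lists "Percent change from baseline in P1NP and sCTX at Months 15, 18, 24, and 36" and "Percent change from baseline in iPTH and sclerostin at Months 15, 18, 24, and 36" for the primary analysis period. Protocol 10.1.5 lists the same endpoints. SAP 10.7.1 repeats Month 15 among the marker analysis times: "9, 12, 15, 18, 24, and 36 in P1NP, sCTX, BSAP, OC and sclerostin".

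**Sampling.** Protocol 7.3.14 sets up a Month 15 visit (±14 days) for sub-study subjects only. Its procedures include "Fasting blood sample for P1NP and sCTX", plus samples for sclerostin and iPTH.

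**Assignment to visits.** SAP 6.1.1 says that the windows in 13.1.1 "will be used to assign evaluations to a most appropriate nominal visit for analysis and summarization". SAP 13.1.1 adds that there are no gaps between windows, that the result nearest the target day is kept when several fall in one window, and that results not used appear in listings only. SAP 9.2.4 rules out imputation of missing markers.

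**The table.** SAP 13.1.1.6 covers these markers. It has rows for Months 1, 3, 6, 9, 12, 18, 24, 36, 48 and 60, and none for Month 15. The Month 18 row has target Day 548 and window "End of Double-blind Period Date +1 to Study Day 639".

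**The concern.** An endpoint is named, its sample is drawn, and the rule that turns samples into visit results has nowhere to put it. This is a conflict between two parts of the SAP, and more than a missing detail: followed literally, the assignment rule yields an empty Month 15 time point.

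Two things are at stake. First, Month 15 is the first scheduled marker sample after the switch to open-label alendronate. The plan collects it but produces no result from it. Second, the sample does not simply disappear. It sits in the Month 18 window and can be reported as a Month 18 value when nothing closer to Day 548 is available.

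**Working it through.** **Inputs**
- Target days 31, 92, 183, 275, 366, 548, 731, 1096, 1461 and 1826 for Months 1, 3, 6, 9, 12, 18, 24, 36, 48 and 60 (SAP 13.1.1.6).
- "Month is defined as a calendar month", counted from Day 1 (Protocol 7.1.1), with ±14 days for visits after Month 12 (Protocol 7.1.2).
- End of the double-blind period (SAP 6.1.2). Its first two rules apply only up to Study Day 396. The third is "End of study day or Study Day 396, whichever occurs first". The latest possible date is therefore Day 396.
- Assumption: Day 1 dates from 2012 to 2015, a span chosen to cover leap years. The documents do not give it, and its effect is a few days at most.

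**1. Reproduce the table's own bounds.** Taking the midpoint of adjacent targets and rounding down gives all seven fixed upper bounds in the table:
- (31+92)/2 = 61.5 → 61
- (92+183)/2 = 137.5 → 137
- (183+275)/2 = 229
- (275+366)/2 = 320.5 → 320
- (548+731)/2 = 639.5 → 639
- (1096+1461)/2 = 1278.5 → 1278
- (1461+1826)/2 = 1643.5 → 1643

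**2. Where an on-time Month 15 sample falls.** Fifteen calendar months after Day 1 is Study Day 455 to 459. With ±14 days this becomes 455−14 = 441 to 459+14 = 473.

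**3. Which window that is.** The Month 18 window opens by Day 396+1 = 397 at the latest and closes on Day 639. All of Days 441 to 473 lie inside it, and none can fall in the Month 12 window.

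**4. What the nearest-to-target rule does.** A Month 15 sample is 548−473 = 75 to 548−441 = 107 days before target. Eighteen calendar months is Study Day 547 to 551, so an on-time Month 18 sample falls on Days 533 to 565, at most 565−548 = 17 days from target. An on-time Month 18 sample therefore always wins, and the Month 15 result goes to listings. If no closer sample exists, the Month 15 value is kept and labelled Month 18.

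**5. Ceiling on the number affected.** The sub-study plans about 200 subjects. Planned dropout is 10% in the first year and 8% a year thereafter (Protocol 3.3).
- Annual proportions: 200 × 0.90 × 0.92^(3/12) = 176.3.
- Exponential hazards: 200 × exp(−0.10 − 0.08×0.25) = 177.4.

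Both assume that all 200 are in the sub-study by Month 15.

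**6. The missing row, by the SAP's own conventions.** The formula 1 + 365m/12, rounded to the nearest day with halves down, reproduces all 13 post-baseline target days used in SAP 13.1.1 for study visits from Month 1 to Month 60. For m = 15 it gives 457.25, so Day 457. The midpoint with Month 18 is (457+548)/2 = 502.5, a split at 502/503. On-time Month 15 samples (441 to 473) then fall in Month 15, and on-time Month 18 samples (533 to 565) stay in Month 18. A target of Day 458 would move the split to 503/504 without changing either statement.

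**The case against.** **It is a drafting slip that a programmer would catch.** The intent is clear from SAP 4.5, and an empty Month 15 column would be noticed. That is fair, and it is a reason to rate the point as minor. It does not remove the point. No passage exempts these markers from the windows or tells the programmer to use the visit label instead, so the boundary would have to be chosen after the SAP was final.

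**The row may have been lost in the PDF conversion.** It was not. The Month 18 window begins the day after the double-blind period ends, which leaves no days for a Month 15 window.

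**SAP 10.7.1 is weak corroboration.** This stands. The same list attaches Months 15 to 36 to BSAP and OC, which are collected only to Month 12. SAP 4.5 and Protocol 10.1.5 carry the point without it.

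**Stronger readings that the documents do not support**
- *That 176 to 177 results are expected to be lost.* Protocol 3.1 and 7.8.1 let subjects already on trial join the blood-only portion later, using stored samples. The Month 15 visit is for sub-study subjects only, so late joiners may have no Month 15 sample. The figure is a ceiling.
- *That a count of relabelled values can be taken from dropout.* Planned dropout from Month 15 to Month 18 is 1 − 0.92^0.25 = 2.06%, or 0.0206 × 176.3 = 3.6 subjects. This does not bound the number relabelled. Protocol 7.3.16 requires a marker draw at early termination, which would usually be nearer Day 548 and displace the Month 15 value. Missed Month 18 draws would add cases at a rate the documents do not give.
- *That the Month 48 and 60 rows are a further error affecting results.* They sit awkwardly beside Protocol 7.3.18, but the marker endpoints in SAP 4.5 and the analysis times in SAP 10.7.1 stop at Month 36. Those rows feed no stated endpoint.

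**Conclusion.** The SAP is wrong as written on this point, and the consequence is minor. Under SAP 6.1.1 and 13.1.1.6, no Month 15 result is produced for any sub-study subject, although four markers have a stated Month 15 endpoint. Each on-time Month 15 sample either goes to listings only or is analysed as Month 18, 75 to 107 days early.

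The conclusion about the window rests on the calendar-month definition, the ±14-day visit window and the Day 396 cap. The assumed span of Day 1 dates does not affect it, because Day 441 is 45 days past the cap. The number of subjects with a Month 15 sample and the number relabelled as Month 18 cannot be derived from the documents.

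A reader might infer that the trial's main conclusions are touched. They are not. These markers are outside the alpha-controlled sequence, and no fracture or main-study BMD result uses this table. OC and BSAP are also unaffected, because they have their own table (SAP 13.1.1.5), which ends at Month 12.

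**What to change.** In SAP 13.1.1.6:
- Add a Month 15 row with target Day 457 and a window from End of Double-blind Period Date +1 to Study Day 502.
- Start the Month 18 window at Study Day 503 and leave its end at Study Day 639.

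The cost is one added row and one moved boundary in one table. No new data, visits or protocol changes are needed. The change should be made before unblinding, so that the boundary is not chosen with results in view.
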